6.5.2.1 Subgroup Analyses

Subgroup analysis on CBR, ORR and BOR will be performed on FAS as well as Tumor Response Evaluable Set. The following are, but not limited to, potential subgroups for analysis:

- Prior CDK4/6 inhibitor for advanced/metastatic disease (abemaciclib, palbociclib, or ribociclib; Yes, No)
- Baseline ESR1 status (WT, Mutant)

It should be noted that subgroup analyses lead to reduced, often severely reduced, sample sizes in the groups evaluated. This increases the risk for chance findings and interpretation of any results stemming from subgroup analyses should be interpreted with great caution. Only subgroups with adequate cell sizes (i.e. n=5) will be presented in the summaries.

6.5.3 Progression-Free Survival

Progression-free survival (PFS) is a secondary endpoint for all cohorts. It is defined as the time (in months) from the date of first dosing until the date of objective PD (as defined by RECIST version 1.1) or death (by any cause in the absence of progression), whichever occurs earlier: (date of first radiologic PD or death – date of first treatment + 1) / 30.4375.

Subjects who have not progressed or died at the time of analysis will be censored at the time of the latest date of assessment from their last evaluable RECIST assessment prior to receiving another anticancer therapy. If the subject has no evaluable visits or does not have Baseline data, they will be censored at Day 1 unless situation 3, as described in [Table 3](#), is encountered.

The distribution of PFS will be described in tabular format using Kaplan-Meier methodology², reporting estimated median (in months) with 95% CI, 25th and 75th percentiles (Brookmeyer and Crowley 1982, Klein and Moeschberger 1997) and KM estimated probabilities with corresponding 95% CI is (Kalbfleisch and Prentice 2002) at several time points (including 2, 4, 6, 8, 10 and 12 months).

Refer to [Table 3](#) for censoring rules for PFS.

Table 3 Censoring Rules for Progression-Free Survival

Situation	End Date	Censored
1. Documented radiological PD before initiation of non-study anti-cancer treatment (for subjects with missed tumor assessment, check #3)	Date of the first tumor assessment that determined PD	No
1a*. Clinical PD before initiation of non-study anti-cancer treatment (for subjects with missed tumor assessment, check #3)	Date of Clinical Progression	No
2. Death during the study with no prior PD and no prior initiation of non-study anti-cancer treatment (for subjects with missed tumor assessment, check #3)	Date of death	No
3. Radiologic PD or Death after more than one missed tumor assessment	
Date of last adequate tumor assessment prior to missed tumor assessment
 
More than one response assessment is considered to be "missed" if more than 18 weeks (126 days) has elapsed since the last evaluable image-based response assessment (or first dose date if no prior response) up to 24 weeks after C1D1. If the last evaluable image-based response assessment is more than 24 weeks after C1D1, more than one response assessment is considered to be "missed" if more than 26 weeks (182 days) has elapsed. If a subject develops progressive disease or dies after this interval, the tumor response assessment will be excluded from the analysis and censored at the last evaluable assessment.
	Yes
4. Non-study anti-cancer treatment initiated before radiologic PD	Date of last adequate tumor assessment prior to initiation of non-study anti-cancer treatment	Yes

Situation	End Date	Censored
5. Subjects still followed without radiologic PD or death as of cutoff date	Date of last adequate tumor assessment (or date of first treatment if no adequate post-Baseline tumor assessments)	Yes
6. Subjects without adequate Baseline tumor assessment	Date of first treatment	Yes
General Considerations:		

Radiologic PD for RECIST v1.1 is defined as overall response of 'PD'.
 
*As a sensitivity analysis, PFS will also be defined using Clinical progression as equivalent to radiological progression. Please refer to situation 1a. The date of clinical progression is defined as the earliest date of any treatment discontinuation for disease progression, in the absence of radiologic PD.
 
Tumor response assessment dates will be assigned based on the date the image was performed, not the date the image was assessed.
 
An adequate/evaluable tumor assessment is one with an overall response of CR, PR, SD or PD without prior censoring events (anti-tumor therapy, missed visit).
		

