9.4.5.4 PROGRESSION-FREE SURVIVAL

The PFS is defined as the time from date of first dosing until the date of objective disease progression as defined by RECIST v1.1 or death (by any cause in the absence of progression).

Subjects who have not progressed or died at the time of analysis will be censored at the time of the latest date of assessment from their last evaluable RECIST assessment. If the subject has no evaluable visits or does not have baseline data, they will be censored at Day 1 unless they die within two visits of baseline.

If a subject discontinues treatment prior to progression, then these subjects will continue to be followed until evidence of objective disease progression as defined by RECIST v1.1 and their PFS time will be derived as defined above.

If a subject receives a subsequent therapy prior to progression, then these subjects will be censored at the time of the subsequent therapy.

The PFS estimate will be presented using Kaplan-Meier methodology.

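### SAP 6.5.3 contradicts itself on deaths before any evaluable scan: its text censors them at Day 1, while Table 3 and the protocol count them as PFS events

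*SAP*

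**What the plan says.** Protocol 9.4.5.4 deals with subjects who have no evaluable visit or no baseline data: "they will be censored at Day 1 unless they die within two visits of baseline". An early death without scans is therefore a PFS event.

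SAP 6.5.3 keeps the sentence but changes the exception: "If the subject has no evaluable visits or does not have Baseline data, they will be censored at Day 1 unless situation 3" of Table 3 is encountered. The same section defines PFS as ending at progression "or death (by any cause in the absence of progression), whichever occurs earlier", and refers the reader to Table 3 for the censoring rules. The relevant rows are:

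- Situation 2, not censored, dated at death: "Death during the study with no prior PD and no prior initiation of non-study anti-cancer treatment". The row tells the user to check situation 3 where an assessment was missed.
- Situation 3, censored: "Radiologic PD or Death after more than one missed tumor assessment". During the first 24 weeks this means "more than 18 weeks (126 days) has elapsed since the last evaluable image-based response assessment (or first dose date if no prior response").
- Situation 5, censored, for subjects still followed without radiologic PD or death: "Date of last adequate tumor assessment (or date of first treatment if no adequate post-Baseline tumor assessments").
- Situation 6, censored at first treatment: "Subjects without adequate Baseline tumor assessment". No exception for death is given.

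SAP Section 8, which lists changes from the protocol, does not mention this one.

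**The concern.** An exception to a censoring rule should name the cases that are not censored. Here it names a situation whose own outcome is censoring. For a subject with no scan, situation 3 has no earlier assessment to fall back on, so it censors at first dose, which is Day 1 again. The exception therefore changes nothing, and the sentence taken literally censors every subject without an evaluable visit at Day 1, including those who die in the first weeks. Table 3 situation 2 and the protocol make the same deaths events.

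The subjects concerned have the worst outcome. Censoring them at Day 1 takes them out of the risk set before any event, so the error can only raise estimated PFS. The SAP reports PFS from 2 months onward, close to where these deaths fall. Elsewhere it treats a death before the first post-baseline assessment as a non-response for CBR and ORR (SAP 5.2 and 6.5.2), so the literal sentence would also handle the same subjects differently across endpoints.

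**Working it through.** **Inputs.** Scans every 8 weeks, ±7 days, for 24 weeks (protocol 8.1.1). Limits of 126 and 182 days (SAP Table 3, situation 3). N = 75 per dose level (protocol 9.2.3). For illustration only, a median PFS of 4.6 months, which protocol 2.1 gives for placebo plus fulvestrant in the cited randomised trial. The number k of deaths before any evaluable scan is not in the documents and is varied.

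**1. The plan's own limits.** Two 8-week visits plus two 7-day windows: 2 × 56 + 2 × 7 = 126 days. For 12-week visits: 2 × 84 + 2 × 7 = 182 days. Both match Table 3. The 126-day limit is thus the protocol's two visits with windows included; without windows it is 2 × 56 = 112 days. The latest on-time first scan is at 56 + 7 = 63 days.

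**2. The three rules side by side.** Take a death with an adequate baseline, no post-baseline scan and no new anticancer therapy:

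| Days from first dose to death | SAP 6.5.3 text, literal | SAP Table 3 | Protocol 9.4.5.4 |
|---|---|---|---|
| 30, 55, 63 or 112 | censored, Day 1 | event | event |
| 126 | censored, Day 1 | event | event only if windows are included |
| 127 or more | censored, Day 1 | censored, first dose | censored, Day 1 |

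The contradiction is confined to deaths at 126 days or less. That range covers every death before the first scheduled scan.

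**3. Size if the sentence is followed.** Suppose nobody else is censored before the last of the k early deaths, and S subjects are still event-free just after it. With the deaths counted, the Kaplan-Meier estimate there is S/N; with Day 1 censoring it is S/(N−k). Risk sets are identical from then on, so every later estimate is multiplied by N/(N−k):

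- k = 1: 75/74 = 1.014
- k = 3: 75/72 = 1.042
- k = 6: 75/69 = 1.087

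**4. Illustration.** N = 75, with the other N−k subjects following an exponential PFS with median 4.6 months:

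| k | 6-month PFS, deaths counted | 6-month PFS, Day 1 censoring | Median in months, counted | Median in months, Day 1 censoring |
|---|---|---|---|---|
| 1 | 40.0% | 40.5% | 4.51 | 4.51 |
| 3 | 38.7% | 40.3% | 4.33 | 4.51 |
| 6 | 37.3% | 40.6% | 4.05 | 4.60 |

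In a small group one death matters more: at N = 6, the upper size of an escalation cohort, the factor is 6/5 = 1.20.

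**5. Missing baseline.** The protocol's exception also covers subjects without baseline data. In Table 3, a death in such a subject meets situation 2 (event) and situation 6 (censored at first treatment). The SAP does not say which prevails.

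**The case against.** The strongest defence is that Table 3 governs. The section counts death as an event and sends the reader to the table for censoring. Situations 2 and 3 together already express the protocol's exception in days, so a programmer working from the table gets the protocol's answer. This stands for subjects with an adequate baseline. It is why the wording does not support the stronger inference, which a reader might draw, that early deaths will drop out of PFS or that the SAP has abandoned the protocol's rule.

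A second defence is context. The sentence follows one about subjects who have neither progressed nor died, so it may not be meant to reach deaths. That does not rescue it: situation 3 requires PD or death, so the exception would then be empty. The parallel protocol sentence also follows such a sentence and plainly does reach deaths.

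Third, a reader might infer that the exception for missing baseline is lost in both text and table. The table leaves precedence open between situations 2 and 6, which is an ambiguity and not a demonstrated loss. The group should also be nearly empty, since screening imaging is required and evaluable or measurable disease is an inclusion criterion (protocol 1.3 and 5.1).

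Finally, the effect may be small. Eligibility excludes life-threatening visceral disease and requires ECOG 2 or better, so few deaths before the first scan are expected. One death in 75 moves 6-month PFS by 0.5 points in the illustration, against a planned precision of ±12 points for CBR at that sample size. This bears on severity. It does not remove the contradiction, and any error runs in one direction only.

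**Conclusion.** The inconsistency is real and of moderate importance. For a death at 126 days or less from first dose with no evaluable scan, the SAP text read literally and SAP Table 3 assign opposite event status, and the protocol sides with the table (between 113 and 126 days, only if its two visits include the windows).

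The size is conditional on the sentence being programmed in place of the table. Later PFS estimates are then inflated by N/(N−k), which for N = 75 is 1.4% in relative terms with one such death and 4.2% with three. The values of k and the 4.6-month median are assumptions; the factor itself does not depend on the median.

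The documents do not support treating this as a threat to the trial's main conclusions. PFS is secondary and descriptive, and the cohorts are non-comparative. The primary CBR counts death before the first assessment as non-response, DOR requires a response first, and OS counts every death.

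**What to change.** In SAP 6.5.3, do one of two things:

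- restrict the Day 1 censoring sentence to subjects without PD or death; or
- point its exception to situation 2, stating that a death 126 days or less from first dose, with no prior non-study anticancer therapy, is an event at the date of death.

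In Table 3, state the order of precedence among situations 2, 3 and 6, so that a death without an adequate baseline scan follows the protocol's exception. It would help to say there that 126 days is how the SAP reads the protocol's two visits, windows included.

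The cost is a few lines of text, with no new data and no change to the design. Where the table would have been programmed anyway, results for subjects with an adequate baseline do not change.

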CR	No CR or missing	SD
PR	CR or PR	PR
PR	SD or PD or missing	SD
SD	NA – no confirmation needed	SD
PD	NA	PD

Responses recorded after initiation of anti-tumor therapy are not used (not evaluable) nor are PD responses after a missed visit [>126 days has elapsed since the last image-based response assessment (or first dose date if no prior response)] up to 24 weeks after C1D1. If the previous evaluable image-based response assessment is more than 24 weeks after C1D1, a PD response is considered to be "missed" if more than 26 weeks (182 days) has elapsed. In the case of stable disease, measurements should have met the stable disease criteria for a minimum interval of 8 weeks (8 weeks minus the 7-day visit window = 49 days) following the start of treatment.

Duration of SD for subjects with best overall response = SD is defined as the time from the day of first study treatment to the start of radiologic disease progression or death. If the subject does not have a radiological disease progression or death, the duration of SD is defined as the time from the day of first study treatment to the date of the last SD assessment. Taking scheduling of imaging into account, a 1 week window will be utilized such that the threshold for 24 weeks will be $23*7 = 161$ [response date – first dose date +1 ≥ 161].

When the investigator is in doubt as to whether progression of disease has occurred and therefore reassesses the subject at a later date, the date of the initial scan should be declared as the date of progression if the repeat scans confirm progression.

Objective Response Rate (ORR) is a secondary endpoint for all cohorts. It is defined as the percentage of subjects with measurable disease who have at least one confirmed response of CR or PR prior to any evidence of progression (as defined by RECIST v1.1). Subjects who develop PD, intolerable toxicity or death or who discontinue study treatment prior to the first post-Baseline assessment will be classified as non-responders.

Data obtained up until progression, or last evaluable assessment in the absence of progression, will be included in the assessment of ORR. However, any complete response or partial response which occurred after a further anticancer therapy was received will not be included in numerator of the ORR calculation.

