The change from Baseline and percent change from Baseline will be calculated for each response assessment for the sum of target lesion measurements. The best (minimum) percent change from Baseline will be identified for each subject.

For further details regarding response criteria, refer to protocol Appendix 2 – Tumor Response Criteria.

Best overall response will be summarized categorically based on the four RECIST categories: complete response (CR), partial response (PR), stable disease (SD) and progressive disease (PD). The summary will also include a category for unevaluable (NE) subjects if applicable and one for non-responders (NR). PR and CR must be confirmed by repeat imaging at least 4 weeks later with no evidence of progression between confirmation visits.

The clinical benefit rate (CBR) and objective response rate (ORR) estimates will be presented along with the associated Clopper-Pearson 95% CIs.

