6.5.4 Duration of Response

Duration of Response (DOR) is a secondary endpoint for all cohorts. It is defined as the time (in months) from the date of first documented response (that is subsequently confirmed per RECIST version 1.1) until date of documented progression or death in the absence of PD: (date of first radiologic PD or death – date of first response + 1) / 30.4375. The end of response should coincide with the date of progression or death from any cause. The time of initial response will be defined as the latest of the dates contributing to the first visit response of PR or CR.

Subjects who have not progressed following a response at the time of analysis will be censored at the date of last evaluable tumor assessment. Subjects who receive other anticancer therapy prior to documented PD will be censored the day this subsequent therapy started.

DOR will be summarized using Kaplan-Meier methodology² in a tabular format.

The proportion of subjects with a DOR of 6 months or more will be summarized.

Censoring rules used for DOR are the same as the ones for PFS ([Table 3](#)).

If there are a sufficient number of responses (n=10), DOR will be analyzed using the same methodology as PFS.

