8. CHANGES FROM METHODS PLANNED IN THE PROTOCOL

In regard to the Monotherapy Phase 2 Efficacy, section 6.1.7 of the protocol state that efficacy in the Monotherapy Phase 2 will be determined by CBR and results will be combined with those from subjects with similar treatment characteristics (2nd/3rd Line therapy) and treated at the same dose level of ZN-c5 in the Monotherapy Expansion arm. The analysis will simply be done by phase.

An additional population not defined in the protocol, the Tumor Response Evaluable Set has been defined for use in efficacy analyses.

In a Protocol Clarification Letter (15 June 2022), it was announced that study has reached the time point where a data cut-off of 18 May 2022 has been established after the primary objectives of the study have

been met. Beyond this cut-off, only limited information including study drug administration, study drug accountability, and non-serious and serious adverse events were collected in addition to any cases of pregnancy, overdose, or medication error. End of treatment information (reason for discontinuation form only [EOT], not the full visit) and Safety Follow-up information (Date of Visit [DOV] form only, not the full visit) were also collected.

Because this cut-off was adopted by the sites at different dates, subjects who were ongoing may have data reported beyond this cut-off date.

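### SAP Table 3 leaves Non-CR/Non-PD off its list of evaluable responses; read as written, situation 5 censors non-progressing subjects with non-measurable disease at first treatment and lowers Kaplan-Meier PFS

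*SAP*

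**What the plan says.** Protocol 5.1, inclusion criterion 12, admits subjects with either evaluable or measurable disease. For subjects with non-target disease only, Table 11 in protocol 10.4.2 gives Non-CR/Non-PD to those neither in CR nor progressing and keeps NE for incomplete evaluation. Its footnote advises against calling this category stable disease. SAP 6.5.2 follows that scheme: Non-CR/Non-PD lasting at least 24 weeks counts as clinical benefit, and best overall response lists it apart from SD and NE.

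SAP 6.5.3 uses a shorter list for PFS: "An adequate/evaluable tumor assessment is one with an overall response of CR, PR, SD or PD without prior censoring events". Three rows of Table 3 depend on that definition:

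- Situation 5 (no radiologic PD or death at cut-off): "Date of last adequate tumor assessment (or date of first treatment if no adequate post-Baseline tumor assessments"). The text above the table likewise censors a subject with no evaluable visit at Day 1.
- Situation 3 (PD or death after more than one missed assessment): the clock runs for 126 days, or 182 days later on, that "has elapsed since the last evaluable image-based response assessment (or first dose date if no prior response").
- Situation 4 (new anti-cancer therapy): "Date of last adequate tumor assessment prior to initiation of non-study anti-cancer treatment", with no date given if there is no such assessment.

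Kaplan-Meier PFS is to be reported at 2, 4, 6, 8, 10 and 12 months. SAP 8 sets the data cut-off at 18 May 2022, after which "only limited information including study drug administration, study drug accountability, and non-serious and serious adverse events were collected". Tumor assessments are not among the items still collected.

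**The concern.** Take a subject with bone-only disease who stays progression-free for a year on regular scans. For CBR the SAP counts that subject as a success. For PFS, if Table 3 is programmed as written, every one of those scans is inadequate and the subject leaves the analysis at first treatment. A similar subject who progresses at the first scan is an event. Whether follow-up is kept or discarded then depends on the outcome, which is informative censoring created by the rule itself.

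Nothing in SAP 6.5.3 or in protocol 9.4.5.4 puts Non-CR/Non-PD back for PFS. Two programmers could therefore produce different PFS curves from the same SAP, one of them biased. PFS is a secondary endpoint for every cohort and has its own subgroup analyses.

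**Working it through.** **Figures in the plan.** No sample size, power or alpha depends on this rule. The missed-visit limits are consistent: 2 × 56 + 2 × 7 = 126 days and 2 × 84 + 2 × 7 = 182 days.

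**Direction.** The Kaplan-Meier estimate is the product of (1 − d/n) over event times. Situation 5 moves only subjects who have no event. Every d is unchanged and every n is equal or smaller, so the estimate is equal or lower at every landmark, with no assumption about hazards.

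**Inputs for the size**

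| Input | Value | Source |
|---|---|---|
| Scan days | 56, 112, 168, then every 84 | Protocol 1.3, 8.1.1 |
| Non-measurable share f | 23%, range 10–40% | Assumption; bone-only share of the trial cited in protocol 2.1 |
| Median PFS | 4.6 or 9.5 months, exponential, equal hazards | Assumption; same cited trial |
| Follow-up | Uniform over 6–24 months | Assumption |
| Non-target CR | None | Assumption |

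**Formulas.** S(t) = 0.5^(t/median). G(g) is the probability that follow-up reaches day g. p(g) = S(previous scan) − S(g).

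- Corrected rule: at risk G(g)·S(previous scan), events G(g)·p(g).
- Situation 5 alone: events unchanged. A fraction c = 1 − Σ G(h)·p(h) of non-measurable subjects is censored at first treatment: c = 0.172 (median 4.6) or 0.398 (median 9.5). Up to day 168 all subjects are still within follow-up, so the number at risk is S(previous scan) − f·c.
- Situations 3 and 5: non-measurable events after day 126 are also removed, so c = S(112) = 0.574 or 0.765.

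**Worked case, median 4.6 months, f = 0.23, situation 5 alone.** f·c = 0.0396.

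- Day 56: 1 − 0.2421/0.9604 = 0.748
- Day 112: 0.748 × (1 − 0.1835/0.7183) = 0.557
- Day 168: 0.557 × (1 − 0.1391/0.5348) = 0.412; corrected rule 0.435

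**Same case, situations 3 and 5.** f·c = 0.132.

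- Day 56: 1 − 0.2421/0.8679 = 0.721
- Day 112: 0.721 × (1 − 0.1835/0.6258) = 0.510
- Day 168: only measurable subjects remain, so 0.510 × 0.758 = 0.386

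**Results at f = 0.23 (PFS, %)**

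| Median | Rule | Month 2 | 4 | 6 | 12 |
|---|---|---|---|---|---|
| 4.6 | Corrected | 75.8 | 57.4 | 43.5 | 18.9 |
| | Situation 5 | 74.8 | 55.7 | 41.2 | 16.4 |
| | Situations 3 and 5 | 72.1 | 51.0 | 38.6 | 16.8 |
| 9.5 | Corrected | 87.4 | 76.5 | 66.8 | 44.7 |
| | Situation 5 | 86.2 | 74.1 | 63.5 | 39.7 |
| | Situations 3 and 5 | 84.8 | 71.4 | 62.5 | 41.8 |

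**Sensitivity**

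- *Share.* For f = 10/23/40%, the 6-month fall under situation 5 is 1.0/2.3/4.2 points (median 4.6) and 1.4/3.3/6.3 (median 9.5). Under both it is 2.0/4.9/9.6 and 1.7/4.4/9.1.
- *Follow-up, f = 23%, situation 5.* The 6-month fall is 4.6–5.1 points with 6–12 months of follow-up and 0.2–1.0 with 24–36 months. Under both rules it does not depend on follow-up.
- *Unequal hazards, f = 23%.* With non-measurable median 4.6 and measurable 9.5, 12-month PFS goes from 38.8% to 36.8% (situation 5) or 39.6% (both). With the medians reversed, 6-month PFS goes from 48.9% to 43.8% or 40.7%.
- *Median on the scan grid, equal hazards.* It does not move at 10% or 23%. At 40% it moves from day 336 to day 252 (median 9.5, either reading) and from day 168 to day 112 (median 4.6, both only).
- *Subjects affected.* In a dose level of 75, 0.23 × 75 ≈ 17 are non-measurable. Of these, 17 × 0.172 ≈ 3 to 17 × 0.398 ≈ 7 are censored at first treatment under situation 5, and about 10 to 13 under both.

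**The case against.** The strongest objection is that nobody would apply the sentence literally. Situation 6 uses the same word for the baseline scan, which has no response category, so a strict reading would censor every subject at first treatment. The SAP also abbreviates elsewhere. One sentence in 6.5.2 reads "Best overall response will be summarized categorically based on the four RECIST categories", although Non-CR/Non-PD is listed earlier in that section. The 126-day rule there runs from the time that "has elapsed since the last image-based response assessment (or first dose date if no prior response"), without requiring the assessment to be evaluable. The protocol keeps Non-CR/Non-PD apart from NE. This is good evidence that the omission was unintended, and I accept that. It does not repair the definition. Post-baseline scans are what the list is for, and the protocol footnote advises against the obvious workaround of recoding to SD.

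The second objection concerns direction. Situation 3 uses the same term, and if it also removes late events the curve need not fall everywhere. In simulations with n = 75, 23% non-measurable and equal hazards, PFS under both rules was higher than under the corrected rule at one or more planned landmarks in 18–22% of trials. It was higher in 70% when non-measurable subjects progressed much faster (medians 4.6 and 9.5 months). This stands. The certain direction belongs to situation 5 alone, and whether situation 3 applies is unclear from its wording.

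The third concerns importance. The share and the medians are borrowed and follow-up is assumed. A fall of 2.3–3.3 points is about half the sampling standard deviation of 6-month PFS at n = 75 (5.5–5.8 points). SAP 8 drops the pooling with Expansion subjects, so dose levels may be smaller than 75. PFS is descriptive and drives no decision. All of this is correct and limits the weight of the point, but it gives no reason to keep the wording.

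**Conclusion.** The concern holds: Table 3 is wrong as written. Situation 5 and the accompanying 6.5.3 text send non-progressing subjects whose only post-baseline result is Non-CR/Non-PD to first treatment, and this can only lower Kaplan-Meier PFS or leave it unchanged. That conclusion needs no assumption.

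The size does. Over shares of 10–40%, with follow-up of 6–24 months and equal hazards, the 6-month fall is 1.0–6.3 points under situation 5 and 1.7–9.6 if situation 3 is read the same way. It is small when follow-up is long. First-treatment censoring under situations 3 and 4 is an inference, because those rows give no date when no adequate assessment exists.

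For DOR the SAP says: "Censoring rules used for DOR are the same as the ones for PFS". DOR starts from a CR or PR, so little effect is expected there. CBR and the Combination Phase 2 futility rule do not use Table 3. This should be fixed, but it does not threaten the primary analysis.

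**What to change.** In the general considerations of Table 3, define an adequate/evaluable assessment as an overall response of CR, PR, SD, Non-CR/Non-PD or PD. That one phrase corrects situations 3, 4 and 5 together and brings PFS into line with the SAP's own CBR rule. It needs no new data and no protocol change. If the PFS tables have already been produced, the sponsor should confirm and document which rule was programmed, and rerun them if Non-CR/Non-PD scans were treated as inadequate.
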